	occurence	permanently	
> 20 times ULN (Grade 4)	Any	Discontinue regorafenib	
	occurence	permanently	
> 3 times ULN (Grade 2 or higher) with	Any	Discontinue regorafenib	
concomitant elevation of bilirubin > 2 times	occurence	permanently	
ULN		Control liver function every	
		week until resolution or	
		return to baseline	

Termination of Regorafenib:

- -In the event of gastrointestinal perforation or fistula develops
- -In the event of reversible Posterior Encephalopathy Syndrome (REPS)
- -In the event of the appearance of cardiac ischemia and/or infarction

Other toxicities

The other toxicities will have to manage symptomatically, if possible. For any toxicity grade \geq 2 at D15 except alopecia and anemia, the irinotecan will be delayed up to two weeks and the toxicity will have to be grade \leq 1 to perform the course.

ARM B: STIVARGA® (REGORAFENIB)

Dosage changes should be made in 40 mg increments (1 tablet). The recommended daily dose of Regorafenib is 160 mg.

Dose reductions of Stivarga ®
1st reduction: 120 mg
2 nd reduction: 80 mg

Table b

Table 10: Dose modification/Delay for toxicities related to study drug (except handfoot Skin reaction and hypertension)^a

NCI-CTC V5.0	Dose	Dose Modification	Dose for Subsequent Cycles
	Interruption		
Grade 0-2	Treat on time	No change	No change
Grade 3	Delay until <	Reduce 1 dose level ^c	If toxicity remains < Grade 2,

Protocole NEXT-REGIRI -Version 6.0 du 09/11/2023

Page 52 sur 86

	Grade 2 ^b		dose re-escalation can be
			considered at the discretion
			of the treating investigator.
			If dose is re-escalated and
			toxicity (Grade 3) recurs,
			institute permanent dose
			reduction.
Grade 4	Delay until <	Reduce by 1 dose level ^c .	
	Grade 2 ^b	Permanent discontinuation	
		can be considered at	
		treating investigator's	
		discretion.	

a Excludes alopecia, non-refractory nausea/vomiting, non-refractory hypersensitivity and asymptomatic laboratory abnormalities.

Table 11: Dose modifications for hand-foot skin reaction

Skin Toxicity Grade	Occurrence	Suggested Dose Modification
Grade 1: Numbness,	Any	Maintain dose level and institute immediately
dysesthesia, paraesthesia,		supportive measures for symptomatic relief
tingling, painless swelling,		
erythema or discomfort of		
the hands or feet which		
does not		
disrupt the patient's normal		
activities		
Grade 2: Painful erythema	1st	Decreasing dose by one dose level and institute
and	occurrence	immediately supportive measures.

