swelling of the hands or feet		If no improvement , interrupt therapy for a
and/or discomfort which		minimum of 7 days, until toxicity resolves to
affects the patient's		Grade 0-1 ^b

b If no recovery after a 4 week delay, treatment will be permanently discontinued. c Cf table b.

normal activities	No	Interrupt Regorafenib until toxicity resolves to
	improvement	Grade 0-1. When resuming treatment, treat at
	within 7 days	reduced dose levelab
	or	
	2nd	
	occurrence	
	3rd	Interrupt Regorafenib until toxicity resolves to
	occurrence	Grade 0-1. When resuming treatment, decrease
		dose by one additional dose level ^{a b c}
	4th	Discontinue treatment permanently
	occurrence	
Grade 3: Moist	1st	Institute supportive measures immediately.
desquamation,	occurrence	Interrupt therapy for a minimum of 7 days until
ulceration, blistering or		toxicity resolves to Grade 0-1. When resuming
severe pain of the hands or		treatment, decrease dose by one dose levelab
feet, or severe discomfort	2nd	Institute supportive measures immediately.
that causes the patient to	occurrence	Interrupt therapy for a minimum of 7 days until
be unable to work or		toxicity resolves to Grade 0-1. When resuming
perform activities of daily		treatment, decrease dose by one additional
living.		dose level ^{a b c}
	3rd	Discontinue treatment permanently
	occurrence	
a Cf table b		

b If toxicity returns to Grade 0-1 after dose reduction, dose re-escalation is permitted at the discretion of the investigator

c Subjects requiring > 2 dose reductions should discontinue treatment

If no recovery after a 4 week delay, treatment will be discontinued permanently.

For subjects who require a dose reduction for Grade 2 or 3 rash or hand-foot skin reaction (HFSR), the dose of study drug may be increased to the starting dose after one full cycle of therapy has been Administered with the reduced dose without the appearance of rash or HFSR > Grade 1.

The following measurements should be considered for prevention and treatment of hand-foot skin reaction:

Termination of Stivarga®:

- -In the event of gastrointestinal perforation or fistula develops
- -In the event of reversible Posterior Encephalopathy Syndrome (REPS)
- -In the event of the appearance of cardiac ischemia and/or infarction

Suggestions:

Control of calluses

Before initiating treatment with regorafenib:

- Check condition of hands and feet
- Suggest a manicure/pedicure, when indicated
- Recommend pumice stone use for callus or 'rough spot' removal.

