4	Life-threatening consequences (e.g, malignant hypertension, transient or permanent neurologic deficit, hypertensive crisis		Discontinue therapy

BP = blood pressure; NCI-CTCAE=National Cancer Institute-common terminology criteria for adverse events a Subjects requiring a delay of study treatment > 4 weeks should go off regorafenib.

Blood Pressure should be monitored weekly for the first 6 weeks of treatment. The blood pressure will be recorded by the treating physician and entered onto the e-CRF.

Any blood pressure that is out of normal range must be reported to the treating physician. Blood pressure measurements considered out of normal range are diastolic \geq 100 mmHg and systolic \geq 150 mmHg, or a \geq 20 mmHg increase in diastolic measurement if the measurement was previously within normal limits.

b If BP remains controlled for at least one full cycle, dose re-escalation is permitted at the investigator's discretion.

c Subjects requiring > 2 dose level reductions (< 80 mg reduction) should go off regorafenib therapy.

d Cf table a.

The dose modification schedule for treatment emergent hypertension during regorafenib dosing should be followed (see [Table 12]). Subjects' blood pressure (BP) measurements will be monitored and appropriate treatment to effectively control hypertension under regorafenib treatment is strongly recommended.

The selection of anti-hypertensive medication used in this setting should be performed at the investigator's discretion, considering possible site-specific treatment guidelines. All medication should be recorded in the subjects e-CRF.

Table 13: Drug-related liver dysfunction

Elevations of	Occurence	Management
alanine aminotransférase (ALT)		
and/or aspartate aminotransférase (AST)		
≤ 5 times upper limit of normal (ULN) (Grade	Any	Continue treatment by
2)	occurence	Regorafenib. Control liver
		function every week until ALT
		and AST values resolve to < 3
		times ULN (grade 1) or to
		their initial value.
> 5 times ULN AND ≤ 20 times ULN (Grade 3)	1st occurence	Interrupt Regorafenib.
		Control ALT and AST
		values every week until
		they resolve to < 3 times
		ULN or their initial value.
		Resuming treatment: if the
		benefice is superior to the
		risk of hepatic toxicity,
		reintroduce Regorafenib
		and reduce the dose of
		one tablet (40 mg) and
		control liver function every
		week for at least 4 weeks.
	2 nd	Discontinue regorafenib
	occurence	permanently

> 20 times ULN (Grade 4)	Any	Discontinue regorafenib

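### In arm B, symptomatic ALT/AST rises fall under both Table 10 and Table 13, which differ on stopping regorafenib after recurrent grade 3 and after grade 4

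*Combined protocol and SAP*

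**What the plan says.** All of this is in protocol section 6.3, in the part on arm B (regorafenib alone).

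- **Table 10, scope.** The heading reads "Dose modification/Delay for toxicities related to study drug (except handfoot Skin reaction and hypertension". The two excepted toxicities have their own tables, 11 and 12. Footnote a narrows the scope further: "Excludes alopecia, non-refractory nausea/vomiting, non-refractory hypersensitivity and asymptomatic laboratory abnormalities".
- **Table 10, grade 3.** Hold until below grade 2, then "Reduce 1 dose level". If the toxicity stays below grade 2, "dose re-escalation can be" considered by the investigator. If grade 3 then recurs, the instruction is to "institute permanent dose" reduction.
- **Table 10, grade 4.** Hold until below grade 2 and go down one level. "Permanent discontinuation" is an option at the investigator's discretion.
- **Table 10, footnote b** (attached to both holds). "If no recovery after a 4 week delay, treatment will be permanently discontinued".
- **Table 13**, titled "Drug-related liver dysfunction", is set out by multiples of the ALT/AST upper limit and makes no distinction by symptoms. A first grade 3 rise means interruption, with a possible return one tablet lower. A second means a permanent stop. Grade 4 means a permanent stop whenever it occurs.

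In arm A the general non-haematological table (Table 6) does name liver function test abnormalities among its exceptions, so they are left to arm A's liver table (Table 9).

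**The concern.** Three toxicities in arm B have a table of their own, and Table 10's heading excepts only two of them. Footnote a takes asymptomatic laboratory findings out of Table 10 but leaves symptomatic ones in. Those same events are also in Table 13. Neither section 6.3 nor section 8.1 (discontinuation of treatment) gives an order of precedence.

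What is at stake is a hepatic stopping rule in the control arm. A site that applied Table 10 to a symptomatic ALT/AST rise could keep a patient on regorafenib in circumstances where Table 13 requires it to end for good.

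**Working it through.** The plan has no figure to reproduce here. The check is a reading of the two tables side by side, followed by the dose that each implies.

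**Inputs.** Dose levels in arm B are 160, 120 and 80 mg/day, with none below 80 mg (section 6.3, Table b). Dosing is on 21 days of each 28-day cycle (section 6.1). Planned patients per arm: 78 / 2 = 39 (section 9.1).

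**Which events are in both tables.** Drug-related ALT/AST rises with symptoms. Asymptomatic rises leave Table 10 through footnote a. An isolated bilirubin rise is not in Table 13, which counts bilirubin only together with ALT/AST. Table 13's row for that combination is left aside here, because its own wording raises a separate question.

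**Row by row, for a symptomatic drug-related ALT/AST rise:**

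| Event | Table 10 | Table 13 | Result |
|---|---|---|---|
| Grade 2, no bilirubin rise | Continue, no change | Continue, weekly liver tests | Agree |
| First grade 3 | Hold, restart one level lower; re-escalation optional | Hold, restart one tablet (40 mg) lower if benefit outweighs hepatic risk | No material conflict |
| Grade 3 recurring after re-escalation | Permanent dose reduction | Permanent stop | Direct conflict |
| Second grade 3, no re-escalation | No occurrence rule; repeating the grade 3 row gives one further level down | Permanent stop | Conflict, by inference |
| Grade 4 | Hold, may restart one level lower; stop optional | Permanent stop | Optional against mandatory |

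**Dose after the event**, assuming no earlier reduction for another toxicity:

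- Full dose per cycle: 160 × 21 = 3,360 mg.
- Grade 3 recurring after re-escalation: 160 → 120 → 160 → 120 mg/day under Table 10. Per cycle, 120 × 21 = 2,520 mg, and 2,520 / 3,360 = 75%. Under Table 13: 0 mg. This assumes re-escalation to 160 mg and a permanent reduction of one level.
- Second grade 3 without re-escalation: 160 → 120 → 80 mg/day if Table 10's grade 3 row is applied again. Per cycle, 80 × 21 = 1,680 mg, and 1,680 / 3,360 = 50%. Under Table 13: 0 mg.
- Grade 4, where the investigator restarts: 160 → 120 or 120 → 80 mg/day under Table 10. Under Table 13: 0 mg.

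**Patients affected.** The documents give no rate of symptomatic grade 3 or 4 ALT/AST rises, so no number can be computed. The lower bound is 0 of 39.

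**The case against.** The strongest answer is that a specific table governs over a general one. Table 10 contains no hepatic instruction, Table 13 is built on ALT/AST multiples, and a site with a raised transaminase would open Table 13. That is very likely what was meant, and it is the main reason why the point is small. It does not remove the gap. The protocol writes its exceptions out instead of relying on that principle: for hand-foot reaction and hypertension in Table 10, and for liver tests in arm A's Table 6. Table 6 is only a guide to drafting habit, since its grade 4 row (a permanent stop) differs from Table 10's.

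Other objections stand in part:

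- **Grade 4.** Stopping satisfies both tables. A reader might infer that Table 10 orders a restart. It does not; it permits one, and offers the stop in the same cell.
- **Second grade 3 without re-escalation.** Table 10 has no occurrence column, so the 80 mg path is an inference. Only the recurrence after re-escalation is written out, and an investigator reaches it only by first using an optional step that Table 13 does not offer.
- **First grade 3.** A reader might infer that the tables clash here too. Both hold and restart 40 mg lower. Their recovery thresholds nearly match: Table 13 labels a value below 3 times the upper limit as grade 1, and adds the patient's initial value as an alternative. The four-week limit is not peculiar to Table 10 either, because section 8.1 lists a treatment stop of more than four weeks as a reason for discontinuation in both arms. What remains is Table 10's optional re-escalation.
- **Reach.** Footnote a removes asymptomatic rises, and the protocol does not define what makes a laboratory rise symptomatic.

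**Conclusion.** The point holds, and it is minor. As written, Table 10 allows dosing to continue after two kinds of symptomatic ALT/AST event for which Table 13 requires a permanent stop: recurrent grade 3 (explicit after re-escalation, inferred otherwise) and grade 4 (a permitted restart against a mandatory stop). Where they differ, the dose is 75% or 50% of the full cycle dose against none in the grade 3 cases worked above. A grade 4 restart at 120 or 80 mg/day gives the same two percentages. These figures assume no earlier reduction for another toxicity.

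A reader might go further and infer that arm B has no settled hepatic stopping rule, or that the survival comparison is at risk. The documents support neither. Table 13 states the rule clearly, and the fault is an incomplete exception list in the table beside it. The sample size, the 55 required events and the intention-to-treat analysis of overall survival do not depend on it. Few if any of the 39 arm B patients would meet the overlap. That is a judgement from its narrow scope, not a computed figure.

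**What to change.** In the heading of Table 10, after hypertension, add to the exceptions: *and ALT/AST elevations, symptomatic or not (see Table 13)*. Table 13 then governs these events alone.

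This resembles the liver exception in arm A's Table 6 but is narrower on purpose. Excepting all liver tests would leave isolated bilirubin rises in arm B without any rule, because Table 13 does not cover them; with the wording above they stay in Table 10. The limit on long interruptions is still listed in section 8.1.

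The cost is a few words in one table heading at the next amendment, with no change to data collection, sample size or analysis.

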- c If no recovery within 30 days, the treatment will be permanently discontinued.
- d Cf table a.

Table 7: Delay and dose modification during the administration of Regorafenib in case of hand-foot skin reaction

Skin Toxicity Grade	Occurrence	Suggested Dose Modification
Grade 1: Numbness,	Any	Maintain dose level and institute immediately
dysesthesia, paraesthesia,		supportive measures for symptomatic relief
tingling, painless swelling,		
erythema or discomfort of		
the hands or feet which		
does not		
disrupt the patient's normal		
activities		

Protocole NEXT-REGIRI -Version 6.0 du 09/11/2023

Page 46 sur 86

Grade 2: Painful erythema	1st	Decreasing dose by one dose level ^a and
and swelling of the hands or	occurrence	institute immediately supportive measures.
feet and/or discomfort		If no improvement , interrupt therapy for a
which affects the patient's		minimum of 7 days, until toxicity resolves to
normal activities		Grade 0-1 ^{b.}
	No	Interrupt Regorafenib until toxicity resolves to
	improvement	Grade 0-1. When resuming treatment, treat at
	within 7 days	reduced dose levelab
	or	
	2nd	
	occurrence	
	3rd	Interrupt Regorafenib until toxicity resolves to
	occurrence	Grade 0-1. When resuming treatment, decrease
		dose by one additional dose levela b c
	4th	Discontinue treatment permanently
	occurrence	
Grade 3: Moist	1st	Institute supportive measures immediately.
desquamation,	occurrence	Interrupt therapy for a minimum of 7 days until
ulceration, blistering or		toxicity resolves to Grade 0-1. When resuming
severe pain of the hands or		treatment, decrease dose by one dose levelab
feet, or severe discomfort	2nd	Institute supportive measures immediately.
that causes the patient to	occurrence	Interrupt therapy for a minimum of 7 days until
be unable to work or		toxicity resolves to Grade 0-1. When resuming
perform activities of daily		treatment, decrease dose by one dose level ^{a b c}
living.	3rd	Discontinue treatment permanently
	occurrence	
a Cf table a		
1 16 1 16 1 16	. 4 (1)	

b If toxicity returns to Grade 0-1 after dose reduction, dose re-escalation is permitted at the discretion of the investigator

c Subjects requiring > 2 dose reductions should discontinue treatment

Suggestions:

Control of calluses

Before initiating treatment with regorafenib:

Protocole NEXT-REGIRI -Version 6.0 du 09/11/2023

Page **47** sur **86**

Réf interne ICM : ICM-ENR-432 Version : 001 Date d'application : 24/05/2017

- Check condition of hands and feet

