	occurence	permanently
> 3 times ULN (Grade 2 or beyond) with	Any	Discontinue regorafenib
concomitant elevation of bilirubin > 2 times	occurence	permanently
ULN		
		Interrupt Regorafenib until
		toxicity resolves to Grade 0-1.
		Control liver function every
		week until ALT and AST
		values resolve to < 3 times
		ULN (grade 1) or to their
		initial value.

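### Table 13 (arm B) gives two incompatible regorafenib instructions, permanent stop and hold until recovery, for the same combined transaminase and bilirubin elevation

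*Combined protocol and SAP*

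**What the plan says.** Table 13 in section 6.3 covers drug-related liver dysfunction in arm B (regorafenib alone). It has four conditions: ALT and/or AST up to 5 times the upper limit of normal (ULN); above 5 and up to 20 times; above 20 times; and a combined condition, ALT/AST "> 3 times ULN (Grade 2 or beyond) with" bilirubin above 2 times ULN.

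The combined condition applies at any occurrence. Its management column reads, in order:

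1. "Discontinue regorafenib", completed on the next line by the word permanently.
2. After a blank line, "Interrupt Regorafenib until" and then "toxicity resolves to Grade 0-1".
3. Weekly liver tests until the transaminases fall below 3 times ULN or return to their initial value.

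The condition and occurrence cells beside items 2 and 3 are empty, and section 6.4 starts directly after them.

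**The concern.** A permanent discontinuation and an interruption with a recovery end point are different actions, and here both answer the same trigger. An arm B investigator whose patient meets the criterion could follow either line and claim to be following the protocol, so two sites could manage the same event in opposite ways.

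This is a stopping rule for liver toxicity. AST, ALT and bilirubin are measured on a fixed schedule in arm B (section 5.1 footnotes and section 5.3), so the criterion will be checked routinely. What is at stake is patient safety and uniform conduct between sites. Overall survival is analysed by randomised arm (sections 9.2 and 9.3), and no distortion of that analysis is claimed.

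**Working it through.** The point rests on a comparison of texts. The only arithmetic is a count.

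**Step 1. What the second sentence means elsewhere.** I looked for every place in section 6.3 where regorafenib is to be interrupted until toxicity returns to grade 0-1, in the words used in Table 13.

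| Place | Arm | Uses | Directly followed by a resumption step |
|---|---|---|---|
| Table 7, hand-foot skin reaction, grade 2 | A | 2 | 2 |
| Table 11, hand-foot skin reaction, grade 2 | B | 2 | 2 |
| Table 13, last row | B | 1 | 0 |
| Total | | 2 + 2 + 1 = 5 | 2 + 2 + 0 = 4 |

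In Tables 7 and 11 the sentence begins "Interrupt Regorafenib until toxicity resolves to" and continues either "Grade 0-1. When resuming treatment, treat at" a reduced level or "Grade 0-1. When resuming treatment, decrease" by a further level. In 4 of 5 uses, then, it is explicitly a temporary hold. The fifth, in Table 13, is the only one printed beneath a permanent discontinuation.

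**Step 2. How Table 13 itself separates the two actions.** In the row for ALT/AST above 5 and up to 20 times ULN, the first occurrence is an interruption followed by a step that opens "Resuming treatment: if the" and makes restarting depend on benefit and risk. The second occurrence is permanent discontinuation. The table therefore treats interrupting and discontinuing as distinct actions with distinct triggers. The last row combines them under one trigger.

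**Step 3. The arm A counterpart.** The matching row of Table 9 has the same two thresholds, also at any occurrence. It gives permanent discontinuation and weekly liver tests, with no interruption text. Nothing says whether the arms are meant to differ for this event.

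**Step 4. Whether another rule decides it.**

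- Table 10, the general arm B table, excepts only hand-foot skin reaction and hypertension in its title, and its footnote removes asymptomatic laboratory abnormalities. It uses delay and dose reduction at grades 3 and 4, with permanent discontinuation left to discretion at grade 4. It does not say what the last row of Table 13 requires.
- Section 8.1 allows treatment to be stopped at any time in the patient's interest. That limits the consequence but does not interpret the row.

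**Step 5. Scope.** Section 9.1 plans 78 patients as 2 × 39, so the row governs the 39 planned for arm B. That is the size of the arm, not an estimate of how many will meet the criterion.

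**The case against.** The strongest objection is that the conflict may come from reading the PDF by program. Tables in section 6.3 show such damage: Table 12 has lost its grade 1 label, Table 3 has shifted cells, and footnotes of Table 10 appear inside Table 11. The disputed block follows a blank line, has empty leading cells, and pairs an action with monitoring, as a separate row would. Its monitoring sentence matches the first row of Table 13 more closely than the corresponding row of Table 9. A lost label cannot be excluded, and if one was lost the finding falls away.

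It is nevertheless the less likely explanation. The printed transaminase bands leave no range for a missing row to cover, Table 9 has the same four conditions and no fifth, and empty leading cells mark ordinary continuation lines throughout Table 13. A missing condition of another kind remains possible.

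The second objection is that the row has no restart step, dose or benefit-risk condition, so a hold is less completely specified than a permanent stop and the sentence may be leftover wording. The first part is correct: the conflict lies in interrupting until recovery, not in an order to restart. But leftover wording in a stopping rule still has to be removed or explained.

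Third, section 6.1 refers arm B to the manufacturer's product information in Appendix 8, which was not available for this review and might address the event. That limits confidence, but it would not make the protocol's own row consistent.

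**Conclusion.** The row is wrong as written: one trigger carries both a permanent discontinuation and a hold until recovery, and nothing in the text reviewed says which governs. The size is one row of one table, in arm B only, with no count of affected patients because the documents give no frequency for the event.

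The conclusion assumes that no row label or condition was lost between the source table and the text reviewed, and that Appendix 8 does not override the row. Confidence is therefore medium. It is still a must-fix, because a liver-toxicity stopping rule has to give one instruction. No effect on sample size, power or the overall survival analysis follows.

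**What to change.** First compare Table 13 with the source document. If a label or condition is missing only from the extracted text, no change is needed. If nothing is missing, the sponsor's clinical team should reconcile the last row to a single instruction, or state the separate condition under which each applies. They should also confirm whether Table 9 and Table 13 are meant to agree for this event and, if not, say so. No clinical rule is proposed here.

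The check takes minutes. A correction would be a wording change in a protocol amendment, possibly handled as a substantial modification to the ANSM and/or the CPP under section 12.6. Nothing in section 9 needs to change.
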